2.3.3 Justification of Dose

The PD effects after approximately 2 hours of VIT-2763 administration in the VIT-2763-THAL-201 study clearly demonstrated that VIT-2763 acted as an FPN inhibitor, at both dosing regimens and induced a mean baseline-corrected change in TSAT of -26.2% (±18.6%) and -46.8% (±23.6%) for the QD and BID regimens, respectively, after 12 weeks of treatment. The placebo group achieved a mean baseline-corrected change in TSAT of -1.3% (±2.3%) after 12 weeks of treatment. On the other hand, the PD effects did not translate into effects on the ineffective erythropoiesis of treated patients; Hb levels, as well as RBC counts, MCHC, MCV, reticulocyte counts and reticulocyte Hb content did not change after 12 weeks of treatment (IND, Section 1.11.4). Several hypotheses may explain these results; however, the Sponsor believes that an insufficient sustained serum iron restriction in between drug administrations may be the cause for such disconnect. VIT-2763 has a short elimination half-life (2-5 hours) after repeat-dose administration that leads to

insufficient drug concentrations to maintain constant low serum iron levels, in particular when VIT-2763 is applied only QD.

Consequently, in this exploratory Phase 2a study adult subjects will receive for 8 weeks either 60 mg BID VIT-2763 (Cohort 1), 120 mg BID VIT-2763 (Cohort 2), 120 mg TID VIT-2763 (Cohort 3) or placebo (Cohort 4a and 4b) (see Figure 1 and Table 2).

Animal models of SCD with 2 administrations of VIT-2763 during the day, showed significant clinical benefit. However, data obtained from the VIT-2763-THAL-201 study indicate that higher doses or more frequent dosing is required to sustain iron restriction throughout the whole dosing period. Signs of chronic excessive PD effects (i.e., anaemia) can be detected early on; haematological safety parameters will be monitored throughout the study (every 2 weeks). The selected VIT-2763 dose levels and dosing frequencies in this Phase 2a exploratory study are considered to be safe and are intended to explore at its best the potential therapeutic PD range of VIT-2763 in this patient population. Different levels of serum iron restriction (doses of 120 mg, 240 mg and 360 mg) and different fluctuations of induced peak and trough serum iron throughout a 24-hour period (BID and TID) are explored. It is still unknown if a more sustained serum iron restriction (TID) or more fluctuating (BID) serum iron levels translate into better clinical outcomes in SCD. That is the reason why in the current protocol a broad range of doses and dosing regimens is explored.

3. STUDY OBJECTIVES AND ENDPOINTS

3.1 Primary Objective

The primary objective of this study is to explore the effect of VIT-2763 on markers of haemolysis.

3.2 Secondary Objective

The secondary objective of this study is to assess the safety and tolerability of VIT-2763 in SCD patients.

3.3 Exploratory Objectives

- To explore the effect of VIT-2763 on haematological indices and vascular inflammation.
- To explore the effect of VIT-2763 on iron and erythropoiesis related blood parameters.
- To explore the effect of VIT-2763 on patient reported outcomes (pain and quality of life).
- To explore the PK of VIT-2763 using a population PK approach.
- To explore the changes in abnormal RBCs (sickling) assessed by peripheral blood smear.
- To explore the number of VOC episodes and visceral infarctions.

3.4 Primary Endpoint

• Mean change from baseline in haemolysis markers as measured by reduction of indirect bilirubin after 8 weeks of treatment.

3.5 Secondary Endpoints

- Mean change from baseline in haemolysis markers as measured by direct and total bilirubin, LDH, potassium, Hb and free haptoglobin after 8 weeks of treatment.
- Frequency and severity of reported or observed AEs by SOC and PTs using MedDRA coded terms, indicating seriousness criteria and relatedness over 8 weeks of treatment.

3.6 Exploratory Endpoints

- Changes in haemolysis markers as measured by indirect, direct, and total bilirubin, LDH, potassium, Hb, and free haptoglobin, from baseline after 2, 4, and 6 weeks of treatment and 4 weeks after EoT.
- Frequency and severity of reported or observed AEs by SOC and PTs using MedDRA coded terms, indicating seriousness criteria and relatedness up to 4 weeks after EoT.

- Changes in clinical laboratory safety tests (serum biochemistry, safety haematology, and urinalysis) from baseline, 12-lead ECG, physical examination findings, vital signs (blood pressure, pulse rate), and haematological changes due to iron-restricted erythropoiesis after 2, 4, 6, and 8 weeks of treatment and 4 weeks after EoT.
- Changes in haematological indices, including Hb concentration, RBC count, Hct, MCV, MCH, MCHC, CHCM, RBC distribution width, WBC analyses including differential WBC counts, platelet and reticulocyte counts, percentage reticulocytes, percentage hypochromic microcytic RBCs (RBC volume versus Hb scatterplot analysis), from baseline after 2, 4, 6, and 8 weeks of treatment and 4 weeks after EoT.
- Changes in blood inflammatory markers as measured by high sensitivity C-reactive protein, interleukin 1 and interleukin 6, tumour necrosis factor alpha, soluble vascular cell adhesion molecule 1, endothelin-1, soluble platelet-selectin, and xanthine oxidase, from baseline after 2, 4, 6, and 8 weeks of treatment and 4 weeks after EoT.
- Assessment of iron-related parameters and markers of erythropoiesis: changes in total serum iron, serum ferritin, serum transferrin, calculated TSAT, hepcidin, and erythropoietin, from baseline after 2, 4, 6, and 8 weeks of treatment and 4 weeks after EoT.
- VIT-2763 PK parameters (C_{max}, clearance, distribution volume, AUC). Sparse sampling for determination of VIT-2763 plasma concentration following multiple dosing will be obtained from pre-dose to 2 hours, 4 hours and 6 hours post-morning dose at study Visit V4. A population PK approach will be applied to estimate PK parameters.
- Change in patient reported outcomes using ASCQ-Me from baseline after 2, 4, 6 and 8 weeks of treatment.
- Changes in abnormal RBCs (sickling) assessed by peripheral blood smear from baseline after 2, 4, 6 and 8 weeks of treatment and 4 weeks after EoT.
- Number of VOC episodes and visceral infarctions over 8 weeks of treatment and 4 weeks after EoT.

4. INVESTIGATIONAL PLAN

4.1 Overall Study Design

This is a Phase 2a, randomised, double-blind, placebo-controlled, parallel group trial in SCD subjects. Multiple doses of VIT-2763 will be administered at 3 dose levels and with 2 different dosing frequencies (60 mg BID, 120 mg BID, 120 mg TID).

A total of 24 subjects with confirmed diagnosis of SCD will be randomised into 4 cohorts (either VIT-2763 or corresponding placebo) (see Figure 1 and Table 2) through a secure and validated centralised IWRS that automates the random assignment of treatment groups to randomisation numbers. Stratified randomisation (balanced allocation across treatment groups) will be used according to genotype (HbS/S - HbS/ β T0).

At baseline, subjects will be assigned to 60 mg BID VIT-2763 (Cohort 1), 120 mg BID VIT-2763 (Cohort 2), 120 mg TID (Cohort 3) and placebo (Cohort 4a and 4b). If more than 1 subject in any dose cohort withdraws or drops out between signing informed consent and the V6 visit, the subject will be replaced until at least 5 subjects, with no major protocol deviation impacting the primary objective of the trial, per treatment/placebo (Cohorts 4a and 4b) arm have passed Visit V6.

Subjects eligible for randomisation will receive a randomisation number. Randomised subjects who terminate their study participation for any reason, regardless of whether the IMP was taken or not, will retain their randomisation number. The next subject will be given the next randomisation number.

An independent DSMB will oversee the safety and conduct of the trial on an ongoing basis. The DSMB will be comprised of medical and statistical representatives. The DSMB can provide recommendations to the Sponsor regarding stopping the study or discontinuing a treatment arm or otherwise modifying the study design or conduct. The DSMB will review safety data on a periodic, but also as needed on an ad-hoc manner, basis as defined in the DSMB Charter.

Treatment stopping rules for individual subjects are defined in Section 5.4.2.

The expected duration of subject participation is a maximum of 16 weeks: a non-treatment screening period of a maximum of 4 weeks (28 days), an 8-week treatment period and a 4-week safety follow-up period. The schedule of assessments is provided in Table 1.

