12. STATISTICAL ANALYSIS

12.1 Statistical Methods

All statistical analyses will be performed using SAS Version 9.4 or later (SAS Institute Inc. SAS/STAT, Cary, NC). The detailed methodology for summary and statistical analyses of the data collected in this trial will be documented in a SAP that will be finalised prior to database lock and the unblinding of the study.

For continuous parameters, summary statistics will include the number of subjects, mean, standard deviation, quartiles, minimum and maximum, and the 95% confidence interval of the mean (if appropriate). For categorical parameters, summary statistics will include counts, percentages, and the 95% confidence interval of the percentages (if appropriate) in each category.

Summary statistics will be provided on overall subjects receiving VIT-2763, by dose and for all subjects receiving placebo. Subjects from Cohort 4a and Cohort 4b will be combined into 1 placebo group.

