12.2 Sample Size and Power Calculations

No specific sample size calculations have been performed for this study.

It is planned to randomise 24 subjects in a 3:3:3:2:1 ratio into 3 VIT-2763 dose groups and 2 placebo groups.

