12.3 Randomisation

All subjects enrolled must be identifiable throughout the study. The Investigator will maintain a list of subject numbers and subject names to enable records to be found at a later date.

Randomisation of the subject will be performed before start of treatment with IMP using a validated centralised IWRS. Stratified randomisation (balanced allocation across treatment groups) will be used according to genotype (HbS/S - HbS/ β T0).

Subjects eligible for randomisation will receive a randomisation number. Randomised subjects who terminate their study participation for any reason regardless of whether the IMP was taken or not, will retain their randomisation number. The next subject will be given the next randomisation number.

Subjects included to replace subjects who withdraw or drop out or with major protocol deviations impacting the primary objective of the trial, will be assigned to the same cohort as the subjects they are replacing.

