2.5 Randomisation and Blinding

Upon completion of the baseline visit procedures/assessments, it is planned to randomise 24 subjects in a 3:3:3:2:1 ratio into 3 VIT-2763 dose groups and 2 placebo groups.

For randomisation IWRS will be used, a validated centralised procedure that automates the random assignment of treatment groups to randomisation numbers. Stratified randomisation (balanced allocation across treatment groups) will be used according to genotype (HbS/S - HbS/βT0).

Subjects eligible for randomisation will receive a randomisation number. Randomised subjects who terminate their study participation for any reason regardless of whether the IMP was taken or not, will retain their randomisation number. The next subject will be given the next randomisation number. A subject can only be randomised once. Randomised subjects who withdraw consent for further follow-up cannot be re-screened. Re-screening may be considered at the discretion of the Investigator and in consultation with the sponsor at a later point for subjects who fail to meet the protocol eligibility criteria. In such a case, the re-screened subject will be allocated a new screening number.

If more than 1 subject in any dose cohort withdraws or drops out between signing informed consent and the V6 visit, the subject will be replaced with a number randomization number until at least 5 subjects, with no major protocol deviation impacting the primary objective of the trial, per treatment/placebo (Cohorts 4a and 4b combined) arm have passed Visit V6. Subjects included to replace subjects who withdraw or drop out or with major protocol deviations impacting the primary objective of the trial, will be assigned to the same cohort as the subjects they are replacing.

The randomisation schedules, as described in Biostatistics Addendum Subject Randomisation List (BA-S) V2.0 dated 16 March 2022, will be generated and maintained by ALMAC Clinical Technologies. The schedule and the seed will be sequestered until the study database is locked and the study is unblinded. Data will also be unblinded for closed sessions of DSMB meetings.

2.5.1 *Interim Analysis*

No interim analysis is planned.

2.5.2 *Data and Safety Monitoring Board*

An independent Data and Safety Monitoring Committee (DSMB) will oversee the safety and conduct of the trial on an ongoing basis. The DSMB will be comprised of medical and statistical representatives. The DSMB members will be unblinded.

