4.3 Per-Protocol Set

The per-protocol set (PPS) consists of all subjects who, in addition to the ITT criteria, completed the study and had no major protocol deviations impacting the primary objective of the trial (as defined in the protocol deviation plan and finalised during the blind data review meeting). Subjects with a study drug compliance (see Section 5.6) lower than 80% of prescribed doses or upper than 110% of prescribed doses will be considered as major deviations.

Subjects who did not complete the study as per protocol as indicated in study termination CRF form or who discontinued the treatment prematurely as recorded in treatment termination form will be considered as not having completed the study and will then be excluded from PPS in addition to subjects with major protocol deviations. The subjects will be analysed based on the treatment they were randomised to.

4.3.1 *Protocol deviations*

All subjects with major protocol deviations impacting the primary objective as defined in the latest protocol deviations plan will be excluded from PPS. They will be reviewed during the blind data review meeting.

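### Replacement is triggered by withdrawals per cohort but aims at five deviation-free subjects per arm, so placebo can end at 4 untriggered if 4a and 4b count as separate cohorts

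*Protocol*

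**What the plan says.** Protocol 12.2 fixes the size: "It is planned to randomise 24 subjects in a 3:3:3:2:1 ratio into 3 VIT-2763 dose groups and 2 placebo groups". Protocol Table 2 gives Cohorts 1, 2 and 3 six subjects each, Cohort 4a four and Cohort 4b two. There is no sample size calculation.

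The synopsis, Protocol 4.1 and SAP 2.5 share one replacement rule, which has two parts.

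- **Trigger:** "If more than 1 subject in any dose cohort withdraws or drops out between signing informed consent and the V6 visit".
- **Target:** "the subject will be replaced until at least 5 subjects, with no major protocol deviation impacting the primary objective of the trial", reached "per treatment/placebo (Cohorts 4a and 4b) arm have passed Visit V6". The SAP's version of the last phrase is "per treatment/placebo (Cohorts 4a and 4b combined) arm have passed Visit V6".

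Protocol 12.1 also pools placebo for analysis: "Subjects from Cohort 4a and Cohort 4b will be combined into 1 placebo group".

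Protocol 12.3 describes the replacements as "Subjects included to replace subjects who withdraw or drop out or with major protocol deviations impacting the primary objective of the trial" and puts them in the same cohort as the subject replaced. SAP 2.5 carries the same sentence. Neither gives a count that starts the replacement of a deviator. SAP 4.3 includes non-compliance among the deviations: study drug compliance "lower than 80% of prescribed doses or upper than 110% of prescribed doses will be considered as major deviations".

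**The concern.** The trigger counts withdrawals only, within a cohort. The target counts subjects who pass V6 without a major deviation, within an arm. A rule built this way delivers its target only where the two counts coincide. They differ in two places: placebo is one arm made of two cohorts, and a completer with a major deviation counts against the target but not toward the trigger.

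Five per arm is the only minimum arm size the plan states for the Week 8 endpoint, and placebo is the only concurrent reference group. The IWRS also needs a rule that can be programmed in one way.

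**Working it through.** **Inputs from the documents.** Total 24, ratio 3:3:3:2:1, trigger of at least 2 withdrawals in one cohort, target of 5 per arm. The ratio reproduces the cohort sizes: 24 × (3, 3, 3, 2, 1)/12 = 6, 6, 6, 4, 2, which sum to 24.

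**Assumed inputs.** The documents give no withdrawal or major-deviation rates. The rates below are illustrations, with subjects taken as independent.

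**Step 1: withdrawals only, active cohort of 6.** One withdrawal leaves 5 and the target is met. Two withdrawals trigger replacement. There is no gap.

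**Step 2: withdrawals only, placebo, 4a and 4b separate.** One withdrawal in each leaves 3 + 1 = 4, and neither cohort has more than one. This is the only untriggered withdrawal pattern below 5. It covers 4 × 2 = 8 of the C(6,2) = 15 ways (53%) to lose exactly two of the six placebo subjects.

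With withdrawal probability p, P = [4p(1−p)³] × [2p(1−p)]:

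| p | 4a term | 4b term | P |
|---|---|---|---|
| 0.10 | 0.2916 | 0.1800 | 5.2% |
| 0.15 | 0.3685 | 0.2550 | 9.4% |
| 0.20 | 0.4096 | 0.3200 | 13.1% |

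At p = 0.05 and 0.30 the result is 1.6% and 17.3%.

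**Step 3: effect on the primary summary.** SAP 5.7.1 reports a 95% CI of each group mean. In SD units its half-width is t(0.975, n−1)/√n.

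- n = 5: 2.776/√5 = 1.24
- n = 4: 3.182/√4 = 1.59
- Ratio: 1.59/1.24 = 1.28, or 28% wider

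This assumes that the withdrawn subjects contribute no Visit 6 value and that every remaining subject does.

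**Step 4: major deviations, arm of 6.** Under the trigger as worded, one withdrawal plus one deviating completer leaves 4 deviation-free. So do no withdrawals plus two deviators. More deviators leave fewer, so 4 is not the floor.

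For an active cohort with withdrawal rate w and deviation rate m among completers, the chance of fewer than 5 deviation-free completers with no trigger is the sum over a = 0, 1 of C(6,a) wᵃ(1−w)⁶⁻ᵃ × P[Bin(6−a, m) ≥ 2−a].

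- w = 0.10, m = 0.05: 0.531 × 0.033 + 0.354 × 0.226 = 9.8%
- w = 0.10, m = 0.10: 0.531 × 0.114 + 0.354 × 0.410 = 20.6%

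For at least one of three active cohorts, 1 − (1 − P)³ gives 27% and 50%. These figures describe the deviation-free count and the per-protocol set only. In the ITT summary, one withdrawal plus one deviating completer leaves 5 subjects and two deviators leave all 6.

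**Step 5: which change closes which gap.** Counting deviators as well closes the active-arm route but leaves the placebo split across 4a and 4b open. Pooling 4a and 4b closes the withdrawal-only placebo route. Doing both leaves no combination below 5 without a trigger.

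**The case against.** **Placebo may already be one cohort.** Protocol 4.1 speaks of four cohorts, SAP 4.1 labels placebo as Cohort 4, and SAP 5.7.3 numbers the randomised cohorts 1 to 4. On that reading, one withdrawal in 4a plus one in 4b is more than one, and replacement starts. This stands as a possible reading. Against it, Protocol Table 2 lists 4a and 4b as separate cohorts with their own n, Protocol 6.5 counts five groups, and SAP 5.1.5 refers to pooling two placebo cohorts. The text does not settle it.

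**Deviators may already be replaced.** If the sentence in Protocol 12.3 and SAP 2.5 is taken as authority to replace them, the active-arm route closes. It gives no count, so it cannot be applied as a trigger, and it does not close the placebo route. A reader might infer that Protocol 12.3 conflicts with the SAP. It does not: SAP 2.5 contains the same sentence, so the inconsistency is inside SAP 2.5, as well as between Protocol 4.1 and 12.3.

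**The primary analysis keeps deviators.** This stands in full. A reader might set the 27% to 50% figures beside the 28% wider interval and conclude that the primary result is at that risk. The ITT population is analysed as randomised and retains deviating completers, so the widening from 1.24 to 1.59 SD belongs to the placebo split alone.

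**Other stronger readings.** One might read the phrase about dose cohorts as leaving placebo out altogether, but the same sentence sets a placebo target. One might object that the window opens at consent, but a subject who leaves before randomisation belongs to no cohort and cannot be counted in one. One might speak of a weakened primary comparison, but SAP 3.1 and 3.2 define no test or decision rule and call all analyses descriptive.

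**Conclusion.** The point holds in a limited form. As written, the replacement rule does not guarantee its own target of five per arm.

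- **Placebo:** provided 4a and 4b are separate cohorts, one withdrawal in each leaves 4 with nothing triggered. The probability is 5.2% to 13.1% at assumed withdrawal rates of 10% to 20%. The consequence is a placebo CI about 28% wider than at five subjects, in the primary ITT summary.
- **Deviation-free count:** any arm can fall to 4 or fewer untriggered, because the trigger omits major deviators. This affects the per-protocol set and the stated target, not the ITT primary analysis.

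No error rate, power or formal decision depends on it. It is a modest, cheaply corrected inconsistency in a small descriptive study, and it should be reconciled.

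**What to change.** Put one rule, in the target's own unit, in the synopsis, Protocol 4.1, Protocol 12.3 and SAP 2.5. For example:

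*Once an arm's planned six subjects are randomised, a replacement is randomised whenever the number of its randomised subjects who have passed, or can still pass, Visit V6 without a major deviation impacting the primary objective falls below 5. The arms are Cohort 1, Cohort 2, Cohort 3, and Cohorts 4a and 4b combined.*

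SAP 4.3 finalises deviations at the blind data review meeting, which may be too late to replace anyone. They therefore need to be classified on an ongoing, blinded basis while enrolment is open, with the per-arm count held in the IWRS.

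The cost is wording in both documents, an IWRS setting, earlier deviation review, and occasionally one or two extra subjects, which the existing target already implies. If the sponsor does not want those subjects, restate the target as what the trigger guarantees. Counting withdrawals only and taking 4a and 4b as separate, that is at least 5 past V6 in each active arm and at least 4 in pooled placebo, with no guarantee on deviations.

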4.2 Duration of Subject Participation and Study

The expected duration of subject participation is a maximum of 16 weeks, including a non-treatment screening period of up to 4 weeks (28 days), an 8-week (56±4 days) treatment period and a 4-week (28±4 days) safety follow-up period.

The overall end of trial is defined as the date of the last visit of the last patient participating in the trial and the end of patient data collection.

5. SELECTION AND WITHDRAWAL OF SUBJECTS

5.1 Number of Subjects

No specific sample size calculations have been performed for this study.

It is planned to randomise 24 subjects in a 3:3:3:2:1 ratio into 3 VIT-2763 dose groups and 2 placebo groups (Cohorts 4a and 4b).

5.2 Inclusion Criteria

The following inclusion criteria must be met for each subject:

- 1. Subject has provided the appropriate written informed consent before any study-specific procedures are performed including screening procedures.
- 2. Ability to understand the requirements of the study and abide by the study restrictions, and agreement to return for the required assessments.
- 3. Male or female subjects with confirmed diagnosis of SCD, including only HbS/S or HbS/βT0 genotype.
- 4. Subjects who had at least 1 and no more than 10 VOC episodes reported within 12 months prior to screening. Note: A VOC episode is defined as a documented episode of acute chest syndrome or acute painful crisis for the main indication of SCD, which led to health-professional instructed prescription or use of opioids (excluding codeine) for moderate to severe pain.
- 5. 18 to 60 years of age inclusive at the time of screening.
- 6. Body weight \geq 40 kg and \leq 120 kg at screening and baseline.
- 7. Absolute reticulocyte count or percentage reticulocyte count $>1.5 \times ULN$ during screening.
- 8. Subjects on concomitant hydroxyurea treatment must be on a stable dose (mg/kg) for ≥3 months prior to screening Visit V1. There should be no planned dose adjustments during the course of the study in the opinion of the Investigator.
- 9. Female subjects of childbearing potential, must have negative pregnancy tests at screening (serum pregnancy test) and before randomisation (urine pregnancy test), must have stopped breastfeeding as of first dose, and must either commit to true abstinence from heterosexual contact (which must be reviewed on a monthly basis and source documented) or must be willing to use adequate contraceptive precautions, i.e., highly effective method of birth control. Abstinence should only be used as a contraceptive method if it is in line with the subjects' usual and preferred lifestyle, and periodic abstinence (calendar, symptothermal, postovulation methods) is not an

acceptable method of contraception. Female subjects must agree to use adequate contraception during the study and until at least 1 week after the last dose of IMP or requirements from other co-medications taken, e.g., hydroxyurea or according to local requirements, whichever is longer. Effective contraception (highly effective method of birth control, i.e., with a failure rate of <1% per year, when used consistently and correctly) such as implants, injectables, combined oral contraceptives (see below), intrauterine devices, sexual abstinence, or vasectomised partner must be used. Non-childbearing potential includes being surgically sterilised at least 6 months prior to the study.

Note: For female subjects participating in this study, continuous use of hormonal contraception alone is not sufficient, because potential interactions via CYP enzymes may alter the efficacy of hormonal contraception. The continuous use of hormonal contraception by a female subject should be combined with the use of a condom with spermicide or adequate and approved alternatives by the (fertile) male partner.

